1.3 BACKGROUND ON NEOD001

Prothena Therapeutics Limited (Prothena) is developing NEOD001, a humanized immunoglobulin G1 (IgG1), kappa version of 2A4, the parent murine monoclonal antibody, which is directed against a cryptic epitope on amyloid fibrils. NEOD001 specifically targets misfolded light chain aggregates and amyloid deposits. Nonclinical studies to date suggest little cross-reactivity of the antibody with normal immunoglobulins of the immune system. NEOD001, administered by intravenous (IV) infusion, is proposed for use to target the misfolded light chain protein in subjects with AL amyloidosis. See the current NEOD001 Investigator’s Brochure for detailed nonclinical and clinical information.

The proposed mechanism of action for NEOD001 is thought to be two-pronged (Figure 2). First, is the direct interaction of NEOD001 with soluble aggregates resulting in the neutralization of the soluble, toxic aggregated moieties. The second is clearing the insoluble toxic amyloid deposited in organs/tissues. Here, it is believed that NEOD001 attaches to the amyloid deposits and the intact Fc portion of NEOD001 signals monocytes/macrophages to the area; and via phagocytosis, clearance of the insoluble, toxic deposits occurs (e.g., opsonization of the deposited amyloid). It is believed that both mechanisms may contribute to potential clinical benefit.

Figure 2 Proposed Mechanism of Action for NEOD001

Because NEOD001 and 2A4 (the parent murine monoclonal antibody for NEOD001) recognize a conserved epitope in both the AL and serum amyloid A (AA) proteins, nonclinical efficacy was evaluated in mouse models of both systemic serum AA amyloidosis (H2/hIL-6 Transgenic Rapidly Inducible Amyloid Disease [TRIAD] mouse model) and AL (amyloidoma xenograft model) using, 2A4. In the AL xenograft model, treatment with ~5 mg/kg of 2A4 subcutaneously, 3 times a week resulted in a statistically significant reduction in the size of the amyloidomas that were formed (by weight and volume). Efficacy studies in the TRIAD mouse model at the same dose demonstrated improvements in survival and, in some experiments, reductions in amyloid load. A single experiment using high doses of 2A4 (40 mg/kg) at either 1 week after disease induction vs. 3 weeks after disease induction (when organ amyloid burden is well established) generated conflicting results; with increased organ amyloid burden in the early treatment arm, but decreased organ amyloid burden in the late treatment arm. At this time, no explanation for these differences has been found.

Imaging, autoradiography, and biodistribution studies demonstrated specific binding of NEOD001 and 2A4 to their amyloid target in the TRIAD and AL xenograft models. No evidence has been found that would indicate relevant off-target binding of NEOD001 (e.g., to endogenous parent proteins of the amyloid), consistent with the results of the human tissue cross-reactivity study with NEOD001 discussed below.

1.3.1 Nonclinical Safety

Nonclinical safety was evaluated in the cynomolgus monkey, the TRIAD mouse model, and an *in vitro* study examining binding to human tissue.

Cynomolgus monkey: Important amino acid contributions to the epitope in AL amyloidosis are glutamic acid (E) and aspartic acid (D) at positions 81 and 82, respectively, on IgG light chain and these are conserved in this species; i.e., the incidence of E and D at these positions is >90% in both cynomolgus monkey and human. Though the aspartic acid is buried in the normally folded light chain, if physiologic conditions arise that result in the revealing of this epitope, or if there is binding to similar epitopes on other proteins, then the consequence would be evaluable in this species.

In a 28-day, weekly IV dose study of NEOD001 in cynomolgus monkeys with a 28-day dose-free period for control and high dose animals, treatment was well tolerated at all dose levels (10, 50, and 100 mg/kg/week). There were no NEOD001-related changes in any of the study parameters evaluated and thus the no-observable-adverse-effect-level for NEOD001 in this species was 100 mg/kg. Serum levels of NEOD001 were maintained throughout the treatment period. The data suggest a low risk of off-target toxicity.

H2/hIL-6 TRIAD mice: The TRIAD mouse model of AA amyloidosis has limitations relative to safety assessment for AL amyloidosis; e.g., (1) this transgenic model overexpresses human interleukin-6 (IL-6), creating a proinflammatory baseline state that is important for disease progression but can confound safety evaluation, (2) the disease state is also promoted by injection with an amyloid extract, called amyloid-enhancing factor (AEF), intended to seed tissue with amyloid, and (3) it involves an amyloid protein (AA) that is different than the one targeted in this population (AL), despite the fact that 2A4 recognizes both proteins. However, this model contributes to the safety assessment of NEOD001 as it is the only nonclinical model available that offers the ability to assess the potential hazards of antibody binding to amyloid embedded in various vital organs, primarily liver, spleen, and kidney. The murine homologue of NEOD001, 2A4, maintains full effector function and was used in these studies.

Two TRIAD mouse studies were used in the nonclinical safety assessment: a 22-day toxicity study by the IV route of administration and a 28-day toxicity study by IV and subcutaneous routes of administration. In addition, a 22-day special immunogenicity/toxicity study in H2/hIL-6 mice (no AEF) was conducted to compare 2A4 against the immunogenic potential of an unrelated protein, bovine serum albumin (BSA). These are detailed in the Investigator's Brochure and the key points are summarized below.

As intended for this disease model, the TRIAD mouse has background pathology. Appropriate controls demonstrated the effect of the IL-6 transgene (plasmacytosis in spleen, thrombus formation in mesenteric vessels) and the effect of the IL-6 transgene with AEF added (amyloid deposition in kidney, liver, spleen, and other tissues; inflammatory infiltrates in the heart; and renal pathology, including tubular degenerative changes and papillary necrosis). Importantly, no additional pathology was observed that was attributable to 2A4 treatment at the doses studied, 4 and 40 mg/kg/week.

In both toxicity studies, mortality was observed acutely following the third weekly dose (Study Day 15) when 2A4 was administered by bolus IV administration. No pathology was present to indicate mechanism of the cause of death. The timing of the adverse reaction being within minutes to hours of the third weekly dose, and the presence of anti-drug antibodies (ADAs), suggest that the effect is an ADA-mediated phenomenon in this model. In animals that survived, there were no adverse effects described surrounding deposited amyloid, or in other tissues. ADA reactions in animal species are not predictive of human responses and therefore these effects are not considered to contribute to human risk assessment (Bugelski et al, 2004; Pimm et al, 1992). Additionally, while it is possible that ADAs might develop, it is not known whether or not this would be associated with any clinical significance.

A special immunogenicity/toxicity study was conducted to explore whether the mortality observed following IV dosing of 2A4 in the TRIAD mouse can be observed with an unrelated, but immunogenic, protein. Nontransgenic/wild-type (WT) mice and H2/hIL-6 transgenic mice (no AEF administered) were treated once weekly by IV administration with 2A4 at 4 mg/kg. The nontransgenic mice showed no systemic effects; however, the IL-6 overproducing mice developed profound signs (decreased motor activity, hunched posture, ataxia, cold to touch) immediately after dosing on Days 15 and 22, replicating what was observed in the TRIAD mouse safety studies above. Mortality and moribundity occurred post dosing on Day 22. Another group of H2/hIL-6 transgenic mice was treated once weekly by IV administration with BSA at 50 mg/kg. A similar clinical course occurred although signs began one week earlier; i.e. after dosing on Day 8 (the second dose). Again, mortality was observed in some animals after dosing on Day 22. This study demonstrates the importance of elevated IL-6 in the morbidity and mortality observed in this model and further demonstrates that the mortality is not unique to 2A4 but can be seen with other proteins that are immunogenic in this mouse model.

Human tissue cross-reactivity: In a human tissue cross-reactivity study of NEOD001 designed to examine potential off-target effects, a limited number of tissues demonstrated any binding. Cytoplasmic staining was observed in the heart, kidney, pancreas, pituitary, and testis. Cytoplasmic staining is generally not considered to be relevant to IV dosing as these sites are not accessible to the administered antibody. Rare to occasional, mild-intensity membrane staining was observed on ductular and tubular epithelial cells of the pancreas and testis, respectively. No pathologic changes were observed in these organs in the repeat-dose studies suggesting limited safety liabilities from potential binding in these tissues. Overall, these data confirm the prediction of a low potential for binding of NEOD001 to normal tissue.

In summary, the available nonclinical data support clinical development of NEOD001 for the treatment of AL amyloidosis. No target organ toxicity has been described. Based on available models, there are limitations on the ability to assess the interaction of NEOD001 with deposited or soluble AL amyloid. The investigations in an AA amyloidosis model (the TRIAD mouse) provide some reassurance that binding of 2A4, an antibody with full effector function, does not appear to adversely react with deposited amyloid in tissue. Nevertheless, monitoring for changes in disease pathology, as would typically be performed in clinical development, is warranted.

1.3.2 Clinical Safety

The safety and tolerability of NEOD001 have been investigated in the Phase 1/2 study (Study NEOD001-001) in the US, and are being investigated in the following ongoing global studies:

- Phase 1/2 open-label extension study (Study NEOD001-OLE001)
- Phase 2b study (Study NEOD001-201)
- Phase 3 study (Study NEOD001-CL002)

Study NEOD001-001 was a Phase 1/2 open-label, dose escalation study of the IV administration of single-agent NEOD001 in subjects with AL amyloidosis, which enrolled 27 subjects in the Escalation Phase in 7 cohorts (evaluating dose levels from 0.5 mg/kg to 24.0 mg/kg) and enrolled an additional 42 subjects in the Expansion Phase. The most frequently reported treatment-emergent adverse events (TEAEs) overall in Study NEOD001-001 (occurring in $\geq 10\%$ of subjects [N=69], regardless of relationship to NEOD001) were fatigue, nausea, upper respiratory tract infection, diarrhea, anemia, blood creatinine increased, dizziness, constipation, cough, headache, edema peripheral, vomiting, pain in extremity, back pain, dyspnea, edema, muscle spasms, rash, and urinary tract infection (Gertz et al, 2016). No confirmed anti-NEOD001 antibodies were detected. No dose-limiting toxicities (DLTs) or related serious adverse events (SAEs) were reported.

Due to the limited number of infusion-site related reactions reported to date, premedication of subjects prior to the start of NEOD001 infusion is not required in the NEOD001-OLE001, NEOD001-201, and NEOD001-OLE251 protocols. As of 30 September 2016, 221 subjects had been dosed in the 4 completed or ongoing studies. In Study NEOD001-CL002 (VITAL), 129 subjects received a total of 534 infusions of blinded study drug (24 mg/kg NEOD001 plus standard of care or placebo plus standard of care). In Study NEOD001-201 (PRONTO), 23 subjects received a total of 51 infusions of blinded study drug (24 mg/kg NEOD001 or placebo). In Study NEOD001-001, 69 subjects received 994 infusions of NEOD001 (up to doses of 24 mg/kg). In the completed Study NEOD001-001, 9 infusion-site reactions were reported (6 subjects) and most (n=7; 78%) were classified as Grade 1. As noted above, 1 subject in the ongoing Study NEOD001-201 experienced an event of vasovagal syncope (characterized by bradycardia, hypotension, and syncope). Another aspect of safety monitoring in studies of NEOD001 has been a required postinfusion observation time ranging from 60 to 120 minutes. In addition to this study, Studies NEOD001-201 and NEOD001-OLE251 allow for flexibility in monitoring time if no reactions are seen after the first 2 infusions, as described in Section 5.3.

Based on the data available to date, NEOD001 has been well tolerated as single-agent therapy in subjects with AL amyloidosis and no clinically significant safety signals have been identified. See the current NEOD001 Investigator's Brochure for detailed clinical information.

1.4 RATIONALE FOR STUDY CONDUCT AND DOSE SELECTION

The rationale for this study is to provide additional treatment with NEOD001 for subjects who complete Study NEOD001-001, and to continue to evaluate long-term safety and tolerability. All subjects in the current NEOD001 trials are being dosed at 24 mg/kg, which will be continued in this study.

2 **OBJECTIVES**

2.1 **PRIMARY**

- To evaluate long-term safety and tolerability of NEOD001

2.2 **SECONDARY**

- To assess the immunogenicity of NEOD001
- To incorporate serum NEOD001 concentrations in a population pharmacokinetic (PK) analysis

2.3 **EXPLORATORY**

- To evaluate overall survival
- To evaluate change in Six Minute Walk Test (6MWT)
- To evaluate general health-related quality of life using the Short Form-36 (SF-36)

3 STUDY PLAN

3.1 STUDY DESIGN

This is a multicenter, Phase 2, open-label extension study. The purpose of the study is to evaluate the long-term safety and tolerability of NEOD001 in subjects with AL amyloidosis who were previously enrolled and treated for at least 9 months in Study NEOD001-001.

3.2 STUDY ENDPOINTS

3.2.1 Primary

- Assessment of the safety and tolerability of NEOD001 as assessed by vital signs, duration of therapy, 12-lead electrocardiograms (ECGs), routine laboratory assessments, and frequency and severity of AEs

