4.5 TERMINATION OF THE CLINICAL STUDY, INVESTIGATOR, OR STUDY SITE

The Sponsor reserves the right to terminate the study, participation of an individual Investigator, or a study site at any time for any reason. Conditions that may warrant termination include, but are not limited to:

- Clinical or administrative reasons
- Discovery of an unexpected, relevant, or unacceptable risk to subjects
- Sponsor's discontinuation of further development of the study drug
- Study drug becomes commercially available
- Failure of the Investigator to comply with the protocol, the requirements of the Institutional Ethics Committee/Institutional Review Board (IEC/IRB) or Competent Authority, the Sponsor's procedures, or Good Clinical Practice (GCP) guidelines
- Inadequate recruitment of subjects by the Investigator

According to the study contract, the Investigator also reserves the right to terminate participation in the study.

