The reporting period for SAEs is the period from signing of the ICF through 30 days after the last administration of study drug or last study visit, whichever is later. SAEs reported to the Investigator outside of this reporting period will be reported to the Sponsor or its designee if, in the judgment of the Investigator, there is “a reasonable possibility” that the event may have been caused by the product.

All SAEs will continue to be followed until the end of the study or until such events have resolved or the Investigator, in conjunction with the Sponsor or its designee, deems them to be chronic or stable.

8 **STATISTICAL METHODS AND CONSIDERATIONS**

The final analyses will be based on all subject data collected through study discontinuation.

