2.3. Study Endpoints

2.3.1. Primary Endpoints

The primary study endpoints are the frequency and severity of AEs, changes in laboratory assessments from OLE baseline, and change in vital signs and 12-lead ECGs from NEOD001 baseline and OLE baseline.

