Once visit/individual specific percent of planned dose strength are determined, subjects will be assigned a single average percent of planned dose strength value across all visits to be used for summary statistics in the table.

- Total Number of Dose Reductions will be determined for each subject by the number of times the percent of planned dose was less than 100.

In addition, duration of exposure (months) will be calculated including treatment delays and interruptions as: $(\text{last dose date} - \text{first dose date} + 1) / 30.4375$. Duration will be calculated from the first infusion in the original parent study (NEOD001-001) and separately from the first infusion in the OLE. Each duration of exposure will be summarized using descriptive statistics. The number and percentage of subjects with duration of exposure in the following categories will be summarized:

- <3 months
- ≥ 3 and <6 months
- ≥ 6 and <9 months
- ≥ 9 and <12 months
- ≥ 12 and <15 months
- ≥ 15 months and <18 months
- ≥ 18 months and <21 months
- ≥ 21 months and <24 months
- ≥ 24 months

Additional 3-month intervals may be added based on the available data. The number of total infusions will be summarized with similar categories, replacing months with infusions.

All recorded and derived exposure data will be presented in a by-subject data listing.

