11. CHANGES TO PROTOCOL PLANNED ANALYSES

Additional analyses of safety endpoints are included in this SAP.

Due to the discontinuation of the NEOD001 program, no summary tables or figures will be produced for the efficacy endpoints.

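### Duration of therapy is a primary tolerability measure in the protocol, but the SAP reports it only as raw time on drug, so no summary gives overall persistence on NEOD001 in the extension after the programme stopped

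*Protocol*

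**What the plan says.** Protocol 3.2.1, repeated in the synopsis, gives the primary endpoint as "Assessment of the safety and tolerability of NEOD001 as assessed by vital signs, duration of therapy, 12-lead electrocardiograms (ECGs), routine laboratory assessments", together with adverse events. Protocol Section 8 specifies no analysis of duration; Section 8.2 covers administration listings and total dose.

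The SAP restates the primary endpoints without it: "The primary study endpoints are the frequency and severity of AEs, changes in laboratory assessments from OLE baseline, and change in vital signs", continuing with ECGs. SAP 11, which lists departures from the protocol's analyses, does not mention the omission.

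Duration appears in SAP 9.1 (Extent of Exposure): "In addition, duration of exposure (months) will be calculated including treatment delays and interruptions as" (last dose date − first dose date + 1)/30.4375, once from the first parent-study infusion and once from the first OLE infusion. Then: "Each duration of exposure will be summarized using descriptive statistics", with 3-month categories up to 24 months or more, extendable. There is no event definition, censoring rule or split by reason for stopping.

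The authors knew the programme had ended: "Due to the discontinuation of the NEOD001 program, no summary tables or figures will be produced for the efficacy endpoints" (SAP 11). Protocol 4.5 lists "Sponsor's discontinuation of further development of the study drug" among the grounds for terminating the study, and the opening of protocol Section 8 states: "The final analyses will be based on all subject data collected through study discontinuation".

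**The concern.** A subject who stops because of an adverse event has told us how long the drug was tolerated. A subject still on drug when the sponsor ends supply has told us only that it was tolerated at least that long. As exposure the two durations are equivalent. As evidence of tolerability the second is right-censored, and a mean, median or category percentage that pools the two can be biased downward.

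The primary objective is long-term tolerability, and duration of therapy is the one listed primary measure that speaks directly to staying on treatment. If the SAP 9.1 table is its only summary, a reader cannot tell whether a short median reflects patients leaving the drug or the drug leaving the patients.

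**Working it through.** **1. What the SAP provides on stopping treatment**

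| SAP section | Content | Time-based? | Separates sponsor stops? | All stops combined? |
|---|---|---|---|---|
| 7.1 | Counts and listing of early treatment discontinuation by reason | No | Only if the eCRF has that reason | Yes |
| 9.1 | Raw first-to-last-dose duration | Yes | No | Yes |
| 9.2.2 | Crude count of subjects with any TEAE leading to withdrawal | No | Yes (AE stops only) | No |
| 9.2.8 with 9.2.1.2 | Life-table incidence of AEs leading to withdrawal | Yes | Yes (AE stops only) | No; by SOC and PT |

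No row is at once time-based, able to separate sponsor stops, and overall. The 9.2.8 life table also starts its clock at the first parent-study dose but is computed in the OLE Safety Population. Protocol 4.1 required at least 9 months of parent-study treatment for entry, so these subjects had already come through that part of the clock.

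**2. The SAP's own time-based method**

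No figure for duration of therapy is stated, so the nearest check is the worked example in SAP Table 7. The formula is 1 − Π[1 − d/(n − lost/2)]. Over the twelve intervals it gives 0.0550, as stated; the crude rate is 30/3000 = 0.01, as stated. The SAP thus already takes departures into account for adverse events. It does not do so for duration of therapy.

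**3. Ceiling on the SAP 9.1 duration**

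With 36 doses at 28-day spacing (protocol 6.1.2), a completer scores (35 × 28 + 1)/30.4375 = 981/30.4375 = 32.2 months. A sponsor stop before that gives a smaller value that the table cannot distinguish from a stop for intolerance.

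**4. Illustration of possible size**

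The documents give neither dates nor stopping rates, so every input here is an assumption apart from the approximate N. Set-up: 70 subjects; exponential stopping for the subject's own reasons at 10%, 20% or 30% per year; sponsor stop uniform over a 6-month range of time since first OLE dose; 4000 runs. With p the yearly proportion stopping, the hazard is λ = −ln(1 − p)/12 per month, the true median is ln 2/λ, and the true share stopping before 24 months is 1 − exp(−24λ). For p = 20%: λ = 0.0186, median 37.3 months, share 1 − 0.8² = 36%.

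| Own-reason stopping per year | Sponsor stop (months) | Censored | Raw median | True median | Raw share <24 months | True share <24 months |
|---|---|---|---|---|---|---|
| 10% | 12–18 | 88% | 14.6 | 78.9 | 100% | 19% |
| 10% | 18–24 | 83% | 20.4 | 78.9 | 100% | 19% |
| 10% | 24–30 | 79% | 26.2 | 78.9 | 19% | 19% |
| 20% | 12–18 | 76% | 14.1 | 37.3 | 100% | 36% |
| 20% | 18–24 | 68% | 19.7 | 37.3 | 100% | 36% |
| 20% | 24–30 | 61% | 25.2 | 37.3 | 36% | 36% |
| 30% | 12–18 | 64% | 13.5 | 23.3 | 100% | 51% |
| 30% | 18–24 | 54% | 18.7 | 23.3 | 100% | 51% |
| 30% | 24–30 | 45% | 22.4 | 23.3 | 51% | 51% |

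Three cautions apply. The 100% entries hold by construction, since nobody can pass 24 months if the sponsor stops sooner. True medians above 32.2 months could not be observed under this protocol even without a sponsor stop. And where the stop falls after 24 months, the categories below 24 months are undistorted.

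Kaplan-Meier with censoring at the sponsor stop recovers what is estimable: average 12-month persistence is 0.90, 0.80 and 0.70 for the three rates, matching the true values. It does not manufacture a median; at 20% per year and a stop at 18–24 months, the median is not reached in 96% of runs.

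**The case against.** The strongest reply is that the SAP does what it says. Section 9.1 is an exposure section, raw time on drug is the right quantity for exposure, and the protocol endpoint reads simply as duration of therapy, with no persistence estimand attached. Reasons for stopping are tabulated, and both reasons and exposure are listed by subject. The study is single-arm and descriptive. All of that stands, and it is why the exposure table should be kept.

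A reader might go further and infer that the primary objective gets no valid estimate of tolerability over time. The documents do not support that. SAP 9.2.8 plans cumulative as well as crude incidence of AEs leading to withdrawal, and in the SAP 9.2.1.2 life table a sponsor-stopped subject leaves the risk set without counting as an AE stop. That addresses the part of stopping closest to tolerability. What it lacks is an any-AE cumulative row, a clock starting at OLE entry, and treatment of other stops as competing events.

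A reader might also infer that the SAP labels sponsor-stopped subjects as early stoppers, or that the reported durations mainly reflect enrolment date. Nothing in the SAP equates short duration with intolerance. The second inference needs enrolment and stop dates that the documents do not give.

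Finally, an any-reason discontinuation curve is not a clean tolerability measure either, since it mixes intolerance with death and personal choice. That is fair, and it argues for showing an AE-specific curve beside it.

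**Conclusion.** The concern holds as a gap worth closing, not as an invalid analysis. A measure that the protocol lists as primary was dropped from the SAP's primary endpoints without being recorded, and its only remaining summary pools censored with uncensored durations. No planned summary gives overall persistence on drug from OLE entry.

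The size cannot be determined from the documents, which give neither the number of subjects on drug at the sponsor stop nor their time on drug. It could be small: 22.4 against 23.3 months at 30% per year with a stop at 24–30 months. It could also be large: 14.6 against 78.9 months at 10% per year with a stop at 12–18 months. It vanishes if no subject was stopped by the sponsor before completing treatment. SAP 11 says only that the programme was discontinued; how many durations were cut short is an inference to be checked against the data. Treating the sponsor stop as non-informative censoring is also an assumption, though a reasonable one for a programme-level decision.

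**What to change.** 1. SAP 9.1: keep the exposure table and split it by reason for end of treatment (AE, death, other subject or investigator reason, sponsor termination, completion).
2. Add a Kaplan-Meier estimate of time from first OLE infusion to permanent discontinuation for any reason, including death, but excluding sponsor termination and completion of planned treatment, which are censored. Use last-dose dates for events and censoring alike, to match SAP 9.1. Give 95% CIs only at time points where enough subjects remain at risk, with the minimum stated in advance; if the sponsor stop came before 24 months for everyone, no 24-month estimate is supported.
3. Add an any-AE row for cumulative incidence of AE-related discontinuation from first OLE dose, with death and other non-sponsor stops as competing events.
4. Restore duration of therapy to SAP 2.3.1, or record and explain its removal in SAP 11.

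The cost is some SAP wording, one table and one figure. Dose dates and discontinuation reasons are already collected for SAP 9.1 and 7.1. The documents do not list the eCRF reason categories, so confirm that sponsor termination can be identified there. The downside is the mixed any-reason event, which item 3 offsets.
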